#### 6.4 Treatment Phase and Follow-up Assessments

Patients will record falls in a diary. The diaries will be sent to the study site at the end of each month (or up to 7 days later) until month 12. Patients will be interviewed at the end of each month (or up to 10 days later) to rectify missing data and to ascertain details of falls (see section 2.2), injuries and severity (see section 2.3), and complications (see section 10) by study personnel. If the diary is not send, investigator/physician or study personal will contact the patient.

Patients will visit the study site in person for follow-up evaluations at completion of month 3, 6, 12 (+/- 2 or 4 weeks, see Flowchart, section 6.1) for visit 4, 7, 12. The investigator will send a reminder to the patient. If a patient is not able to come for a study visit, every possible effort is made to collect follow-up evaluations. If feasible, follow-up evaluation can also be conducted at patients home. BBS is assessed and questionnaires are filled in by the trial investigator and/or by the study nurse or the patient (see section 2).

Outcomes measures should be conducted, as far as possible, at a consistent time of the day and consistent to medication cycles, particularly in patients with conditions like Parkinson and Multiple sclerosis, who use medications directly influencing mobility and balance.

Attempts should be made to collect all questionnaires for all patients. Particularly the "standard care alone" patients should get special attention by the investigators to reduce loss of follow-up

in this group. However, if the patient declines to complete the questionnaires, this should be documented in the CRF.

Patients should be given sufficient space and time to complete the study questionnaires and all administered questionnaires should be reviewed for completeness. If missing responses are noted, patients should be encouraged to complete any missing responses.

Investigators must not encourage the patient to change responses reported in questionnaires.

Data obtained from assessments done by the investigator or study nurse, as well as data obtained from patient's fall diary and training diary will be filed with the patient's source documents and documented into the eCRF by designated personnel of the study site (e.g. investigator or study nurse). Patient-reported questionnaires will be stored at the patient's source documents and a duplicate sent to the Clinical Trials Unit in Freiburg.

### **Safety assessments**

Safety will be monitored by collecting information on complications at every visit. For details on complications and their collection see section 10.1.

### **Lost to follow-up**

Patients lost to follow-up should be recorded as such in the CRF. For patients who are lost to follow-up, the investigator should show "due diligence" by documenting in the source documents steps taken to contact the patient, e.g., dates of telephone calls, registered letters, etc.

### **EYT therapists, Tai Chi teachers**

EYT therapists, Tai Chi teachers will document at each group session the patients that have participated. They will document monthly whether they deviated from the manual and the reasons for deviation. They will sign the participation of each session in patient's diary. They will instruct the patients how to report the training in their training diary.

## 7 Premature Termination or Suspension of a Study

### 7.1 Premature termination of one of the treatment arms or the entire trial

The coordinating investigator is under obligation to monitor the progress of the clinical trial with regard to safety-relevant developments and, if necessary, initiate the premature termination of a treatment arm or the entire clinical trial. The coordinating investigator will be supported in this responsibility by the Data Monitoring Committee (DMC).

A treatment arm or the entire clinical trial must be terminated prematurely if:

- the benefit-to-risk ratio for the patients changes markedly,
- the coordinating investigator (German LKP) or the DMC considers that the termination of the trial is necessary,
- indications arise that the trial patients' safety is no longer guaranteed,
- an insufficient recruitment rate makes a successful conclusion of the clinical trial unrealisable/no longer feasible.

If the clinical trial is prematurely terminated, the IEC(s) (where required by the applicable regulatory requirements) will be informed (this is usually done by the coordinating investigator).

### 7.2 Premature termination of the trial at one of the study sites

The investigator and the coordinating investigator have the right to terminate the trial at one of the sites.

The clinical trial can be terminated prematurely at the study site by the investigator if, for instance, unforeseeable circumstances have arisen at the study site which preclude the continuation of the clinical trial, the investigator considers that the resources for continuation are no longer available, the investigator considers that the continuation of the trial is no longer ethically or medically justifiable.

The coordinating investigator can initiate the exclusion of a study site from further participation if, for instance, patient recruitment is inadequate, serious problems arise with regard to the quality of the collected data which cannot be resolved.

Premature termination at one of the study sites does not automatically mean a termination of the trial for already enrolled trial patients. A separate decision on further treatment must be made for each patient, depending on the overall situation. Follow-up of already enrolled trial patients must be ensured. The documentation of already enrolled trial patients will be reviewed for completeness and plausibility. Queries may be raised for further clarification before the study site is closed. These queries must be answered properly by the site. The CA(s) and IEC(s) must be duly notified of the study site's closure, including reasons, within the specified period. The

study site concerned will be closed in stages by the CRA when a decision has been made on the further treatment of the patients concerned.

### **7.3 Premature discontinuation of trial participation for individual patients**

The trial patient can withdraw consent for trial participation e.g. consent for the follow-up visits and documentation at any time, without having to give reasons.

The responsible investigator may only withdraw a patient from participation in the trial for the following reasons:

- Extreme circumstances arise which make any trial-relevant follow-up impossible

The documentation should be completed as far as possible under these circumstances, e.g. a final examination and documentation according to the protocol (if possible), a documentation of the premature trial termination on the CRF and in the medical record, giving reasons, should be ensured.

### **7.4 Premature discontinuation of trial treatment for individual patients**

The trial patient can have his/her trial treatment terminated prematurely at any time, without having to give reasons.

The investigator responsible for the trial has the right to terminate the treatment of a patient according to the following conditions:

- Adverse events (including intercurrent illnesses) which preclude further treatment with EYT or Tai Chi or make further participation in the clinical trial inadvisable because the informational value of the trial results is impaired.
- Premature termination of the trial treatment is considered to be medically indicated, e.g. because it is subsequently found that inclusion/exclusion criteria were severely violated.
- Continuation of the trial treatment is unacceptable when the risks outweigh the benefits or in case of a significant deterioration of a health condition or a new diagnosis during month 1-6, affecting safety of the patient and participation in group classes.
- Logistical reasons (patient moves to another location).

In the case the trial treatment of a patient has been stopped prematurely, further follow-up visits and the assessment of the trial endpoints are essential to enable an analysis of the full analysis set according to the intention-to-treat principle. Further visits, follow-up and documentation should always be striven for/ensured in this case. This includes the follow-up of primary and secondary endpoints, as well as complications. The time of termination, and the reason for termination should be documented in the CRF.

## 8 Investigational Interventions

After randomised treatment allocation all study patients will be recommended standard care. Patients allocated to EYT and Tai Chi will start with group exercises.

### 8.1 Intervention description and application

*Brief Name:* Eurythmy Therapy (EYT), Tai Chi/Taiji, standard care.

*What:* EYT [12, 13] and Tai Chi [7-10] are mind-body oriented exercise therapies, training body movements as well as concentrative, sensory and mindfulness capacities. They pursue comparable movements, smoothly flowing, creating sensation and awareness of limb movement and balance (see 2.2). Tai Chi is instructed and guided by a trained teacher giving oral instructions and helping with conducting exercises. EYT is instructed and guided by a therapist, demonstrating and helping with exercises; EYT exercises are accompanied by music, phonemes, poems or rhythms. Patients additionally receive oral and written and audio-visual instructions (see study book) on how to practice daily at home between group sessions. Patients will keep a training diary. Each subsequent group session will start with a short appreciating and constructive discussion on the experience with daily exercises, and what was regarded as supportive.

A core set of exercises are described in a manual and in a video handed out as a DVD to the patients to support them for exercises in between the group sessions. These exercises are based on prior studies investigating fall prevention or on recommendations by experts applying them in the target population, and adapted to the balance and motility limitations expected in the study patients. They have been peer reviewed by participating Tai Chi teachers, EYT therapists and external experts. Beyond, therapists and teachers are allowed to individually tailor and modify exercises to the capabilities of the patients.

“Standard care” means: patients will receive a brochure with detailed written evidence-based recommendations to reduce risk of falling, clearly illustrated and prepared to specifically address the age population (*“Gleichgewicht & Kraft – Einführung in die Sturzprävention”* <https://www.bzga.de/infomaterialien/gesundheit-aelterer-menschen/gleichgewicht-und-kraft-einfuehrung-in-die-sturzpraevention/>)). Patients will also be recommended to visit their primary care physician if they have not done so within the last three months, to discuss fall-prevention measures. Besides the guidance of the brochure, primary care physicians have recent evidence-based guidelines on geriatric assessments including fall prevention measures [60], on managing multi-morbidity [61], and polypharmacy [62]. Current guidelines for fall prevention as well as the fall prevention brochure refer to active lifestyle; to specific exercises to improve balance, strength, flexibility, endurance; to medication modification; to safe home environment; to vitamin D supplementation; to safe footwear; to assistive devices; to improving medical conditions, to treat vision impairment, to manage postural hypotension, heart rate and rhythm abnormalities [22, 23]; the fall prevention brochure also provides addresses. Fall prevention

measures will be organized by the primary care doctors (e.g. prescriptions or referrals) or can be conducted by the patients themselves, using the recommendations of the brochure.

Therapists and Tai Chi teacher will receive a refresher training in appreciating, encouraging, non-judgmental communication (see section 9), before commencement of the trial. They also receive written proposals regarding inner attitude and regarding communication in the exercise groups and in challenging situations. In a follow-up internet-based meeting, they have the opportunity to ask questions and get additional advice. They will receive recommendations to support motivation and adherence of patients. This shall help them to encourage patients to participate in group sessions and to regularly exercise at home and to manage challenges of the group situation.

Study personnel will also receive a refresher training in appreciating, encouraging, non-judgmental communication (see section 9), before commencement of the trial. They also receive written proposals regarding communication with the patients, in a long version and as a short memo card. This is meant to help them to support patients participating in the trial and to appreciate their commitment and effort and to address their need for a calm, encouraging, non-judgemental communication.

*Who provides:* EYT will be provided by a certified EYT therapist (at least 5 1/2 years of training according a standardized curriculum, acknowledged by the “Eurythmy Therapy Association” of Germany) and with experience in treating people comparable to the trial population.

Tai Chi will be provided by a teacher, with at least 500 hours training according to a standardized curriculum certified by the “Bundesvereinigung Taijiquan und Qigong-Netzwerk” or by the “Deutscher Dachverband Tai Chi und Qigong” or to an equivalent curriculum or an equivalent of 500 hours of own teaching Tai Chi (e.g. Tai Chi-teacher which have trained before commencement of these curricula or in other countries), and with working experience in instructing people comparable to the trial population.

Therapists and teachers are qualified and experienced in instructing and guiding the exercises. Before commencement of the trial, the therapists and teachers are invited to practice together. If unable to attend or if recruited at a later time, they will be informed by a manual, by investigator and study personnel of the study sites and by other participating therapists and teachers. They can also communicate with each other via Email and in telephone/web conferences before and during the trial.

Therapists and teachers receive a folder containing general instructions, the manual, participation lists, a documentation sheet, the motivational concept and the communication concept and proposal.

Standard care is provided and organized by the patients’ primary care doctor or consultant according to the patient’s own discretion. The brochure “*Gleichgewicht & Kraft - Einführung in die Sturzprävention*” (<https://www.bzga.de/infomaterialien/gesundheit-aelterer-menschen/gleichgewicht-und-kraft-einfuehrung-in-die-sturzpraevention/>) providing detailed evidence-based recommendations to reduce risk of falling and enable safer mobility is provided

by the study sites. It also enables the patient for self-help. Neither therapists nor teacher nor study personal is meant to comment, recommend or dissuade on any standard care measures or any other fall prevention measures.

*How:* EYT and Tai Chi will be provided in one-hour group sessions, á 5 ( $\pm$  1) patients. These group sessions start with an appreciating discussion about practicing (see section 9), followed by practicing the exercises and – if appropriate – ending with a resting time (approximately 15 minutes). Patients are instructed to practice at home at a minimum of 20 minutes on 3 non-class days.

*Where:* EYT and Tai Chi will be provided in appropriate rooms: They should be easily accessible with public transportation, if possible, located nearby the patients (e.g. in retirement homes, meeting places of senior citizens, churches, at the study sites, in doctor's facilities or in rooms provided by EYT therapists or Tai Chi teachers). The room should be accessible for those with disabilities, should support the patients to feel comfortable, to exercise freely (size 50-70 m^2, minimum 36 m^2), friendly bright, quiet, without distraction, properly ventilated and heatable, with no cold stone floor. One chair per patient (stable and safe) has to be provided. Restrooms should be easy accessible, on the same floor.

*When:* EYT and Tai Chi will be provided first twice/week (week 1-12) and then once/week (week 13-24). The intensity is higher in the first 12 weeks (twice per week), taking into account the learning curve, and reduced to once per week during the second 12 weeks when individually practicing has become more routine. Participants are instructed to practice exercises at home.

*Tailoring:* Tai Chi and EYT exercises follow the manuals but are individually tailored to the capabilities of the participants. When exercises beyond the manual are used, this will be documented by the EYT therapists or Tai Chi teacher, together with the reason for using them. In case of significant deterioration of health condition or a new diagnosis during month 1-6, affecting safety of the patient and participation in group classes, the EYT therapist or Tai Chi teacher should contact the investigator whether group sessions should be interrupted.

*How well:* Patients will give feedback at the beginning of each session regarding their adherence to and their experience with practicing at home. Patients will keep training diaries. Patients will visit group sessions. Deviations from the manual will be documented by therapists and teachers.

## 8.2 Additional interventions

Following additional treatments should not be used during the trial:

- EYT in the Tai Chi group and standard care alone group
- Tai Chi, Qigong, Yoga in the EYT group and standard care alone group

All other treatments are allowed. As Tai Chi and EYT are investigated as an add-on to standard care, no interventions are prohibited, except the study intervention (as well as Qigong and

Yoga) in the comparison groups. On the contrary, a brochure providing detailed evidence-based recommendations to reduce risk of falling and enable safer mobility is provided to all patients

## 9 Support of motivation and adherence

Compliance will be assessed by the Investigator and/or study personnel at each patient visit.

A patient diary regarding training will be provided for each patient at visit one and need to be filled in during the entire trial.

Adherence and motivation will be increased by

- appreciating group sessions,
- discussing supporting and avoiding discouraging elements,
- contacting the patients via phone to remind them on their appointment during the first treatment weeks (subsequently, this reminder can be continued depending on the needs of the patients),
- oral, audio-visual and written instructions on how to practice daily at home between group sessions,
- keeping a training diary,
- writing down own goals in the study book,
- starting each group session with an appreciating and constructive discussion on the experience with daily exercises,
- training of investigators, study personnel, therapists, teacher in communication techniques that take regard of motivating factors especially for the older patients (e.g. appreciating, encouraging, non-judgmental, unagitated, giving time, calm),
- a supportive community, giving sufficient time, achievable, individually adapted exercises [26-28].
- Special attention and appreciation is given to all patients, including the patients allocated to “standard care alone”, to address their needs and increase their feeling of being seen and appreciated, and their adherence with study procedures.

A summary of research on motivation of elderly to exercise as well as of personal recommendations by experts in the field of motivating elderly (geriatric care, pedagogy for social gerontology, trainers of fall prevention exercise classes, communication) will be handed out to EYT therapists and Tai Chi teacher.

In summary it recommends to adapt the approach in communication and motivation to the special needs and habits of elderly people. The patients should be informed about the positive effects of exercise. Personal health believe models should be addressed. Self-efficacy should be shown using easy exercises at the beginning, where the patients can already experience success. Exercises for training at home should firstly be simple, and less demanding. Short-term and long-term successes should be named.

The group sessions should create an open and safe atmosphere, where every patient is seen and valued in his actual situation. New exercises can be embarrassing for the patients as they feel shame not doing it right while others are watching. This has to be considered carefully and

appraisal within the group has to be led by the group leader. Patients should be asked for personal goals which they might achieve with the exercise – like going to a special place or helping their grand-children. Individual patient concerns have to be addressed like the fear of falling and injuries. Patients should be individually interviewed, whether a current disease limits exercise and whether this can be treated or if the exercises should be adapted to this condition. Patients should participate in designing and organizing the group session. The patients should have the opportunity to socialize before or after the group session.

Investigators, study nurses, assistants, therapists and Tai Chi teacher will receive a refresher training in appreciating, encouraging, non-judgmental communication, before commencement of the trial. In a follow-up internet-based meeting, they have the opportunity to ask questions and get additional advice. They are handed out recommendations for appreciating, encouraging, non-judgmental communication.

Patients will be compensated for travel costs to exercise and to visits: 90,- € for first 6 months and 20 € for first screening and follow-up. In case the study centre decides to conduct the follow-up visits at the home of the patient, the compensation (20,- € per visit) will then be used for this purpose.

If participation of patients in group sessions depends on reimbursement of travel costs (social welfare, “*Grundsicherung*”, “*Hartz 4*”), up to 15 % of patients regularly visiting EYT- or Tai Chi-group sessions can receive further reimbursement of public transportation costs to visit group sessions (for further details see study site contracts).

## 10 Safety monitoring and reporting

### 10.1 Complications

#### 10.1.1 Definition of complications

Only complications that could arise from the study specific intervention (EYT or Tai Chi or other exercises in the standard care group) will be collected, documented and – in case of serious complications – reported to the Data Monitoring Committee, DMC (details see chapter 10.3 and DMC Charter). A complication in the ENTAiER study is defined as any untoward medical occurrence in a trial patient such as any unfavourable and unintended sign, symptom, or disease that is possibly related to the study intervention. As the (non-pharmacological) intervention (EYT and Tai Chi) is training of musculoskeletal, sensory, concentrative elements, complications can be:

- Injuries caused by falls that happened during exercises in groups or at home.
- Musculoskeletal pain – except aching muscle - (e.g. foot, knee, low back pain, arthritis, joint effusion, reduced joint function), neuralgia, cardiovascular disorders (e.g. dizziness or faintness, symptoms of hypotension or hypertension, syncope, chest pain, cardiac arrhythmia), vertigo, dizziness, fatigue, syncope, dyspnoea, bronchospasm, dyspnoea, neurological cognitive disturbance, confusion, mood alteration, or others.

Not regarded as complications are

- conditions that were already present at the time of informed consent  
aching muscle ('Muskelkater'), which is to be expected.

The expression "related" means, that there is evidence or argument to suggest a reasonable causal relationship between the event and the administration of the intervention, e.g. close temporal connection, exclusion of other causes.

The assessment "not related" is appropriate, if the complication is clearly or most likely explained by other causes even if a potential relationship between treatment and the complication cannot be completely excluded.

Falls and injurious falls will be documented as primary outcomes. In case they happen during exercises in groups or at home, this will be noted. They will also be reported to the study center by therapists or teachers in case that they happen during exercises. Injuries caused by falls that happened during exercises in groups or at home will be documented as complications and indicated as caused by a fall. All falls that happen during exercises in groups or at home will be reported to the DMC with the regular report on complications.

Further information on safety will be referred from the FIMA, assessing health care utilization like physician contacts and hospitalizations at month 3, 6 and 12.

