### 1.3 Safety

EYT and Tai Chi pursue gentle, smoothly flowing movements. Their risk can be assumed to be comparable to normal physical exercise applied to reduce fall risk. Trials investigating exercises for preventing falls in elderly in general report minor harms, including pain, bruising or fall injuries or fractures that occurred during the exercise session. Trials comparing exercise intervention with a control group reported no difference in the rate of serious injuries [40, 46]. No specific risk is associated with EYT and Tai Chi; they are unlikely to result in serious adverse events, but may be associated with minor musculoskeletal aches and pains or other side effects of gentle exercises. One extensive systematic review on safety of Tai Chi identified 153 RCTs, (searched through March 2013), most targeting older adults. Of these, only 50 had included reporting of AEs, and only 18 trials (12% overall) also reported an explicit AE monitoring protocol. Reported AEs were typically minor and expected, and primarily musculoskeletal related (e.g., knee and back pain); no intervention-related serious AEs were reported [47]. Cochrane Reviews on Tai Chi for preventing falls and reducing fear of falling on older people had not identified any risk [7, 8, 40]. A recently published trial on Tai Chi in preventing falls among older adults at high risk of falling had documented 2 falls during classes in 85 community-dwelling adults 70 years or older during 48 60-minute Tai Chi classes. Altogether, in this trial, Tai Chi had reduced the risk of falling [48].

Regarding EYT, no specific side effects are known. In an observational study without a control group, 3.1% (13/419) of patients receiving EYT had noted unspecific adverse reactions to EYT (like symptom aggravation, inner tension, depressed mood) during a period of 24 months. The study team had not assessed a causal relationship of these patient-reported adverse reactions to EYT. None of the patients had stopped EYT due to the adverse reactions [30]. A trial investigating a combined multimodal intervention including EYT in 126 breast cancer survivors with chronic cancer-related fatigue over a 10-week period (140–165 minutes per week) found 87 possible adverse therapy reactions to the multimodal intervention, like ‘back pain’, ‘dizziness during eurythmy’; ‘increasing exhaustion through sleep restriction/stimulus control’ [43]. Beyond, no specific risks are known [12, 13].

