#### 4.1 Inclusion Criteria

- Adults 65 years or older.
- Chronic disease (musculoskeletal, neurologic, internistic)
- Increased risk of falling (Berg Balance Scale (BBS) score 49 or less).
- Self-reported history of imbalance (*Anamnestisch: Unsicherheit beim Gehen oder Stehen*)
- Living in the community (at own home) or retirement or nursing home.
- Ability to participate in 1-hour group-based sessions (medical assessment).
- Able to leave home on their own at least twice per week (e.g. for doctors visit, shopping)
- Patient's written informed consent has been obtained

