#### 14.5.2 Secondary endpoints

For the analysis of the secondary endpoint total number of falls per patient within 6 months after handing out the study book, a negative binomial regression model will be used to test the efficacy of EYT versus Tai Chi versus standard care. Negative binomial is preferred over Poisson regression because of potential overdispersion. Fall rates for patients with follow-up times of less than 6 months will be adjusted by accounting for their exposure time. The model will include intervention type, study site, BBS score, and age as independent variables. Incidence rate ratios (IRR) between interventions will be calculated from the model with two-sided 95% CI. To take into account potentially present excess zeroes, a zero-inflated negative binomial model will be used as a sensitivity analysis

Other secondary endpoints will be analysed with appropriate regression models. Analyses will be repeated for the observation period of 12 months after date of handing out the study book. This also applies to the primary endpoint at 12 months.

As a sensitivity analysis these analyses above will be repeated in the PP.

Safety analyses will be performed in the SAF. Rates of complications will be calculated with two-sided 95% CI.

No formal interim analyses of the efficacy endpoints will be performed.

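### Section 10.1.1 keeps conditions present at consent out of the complications without saying whether their worsening counts, so complication rates may be too low or inconsistent

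*Protocol*

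**What the plan says.** Section 10.1.1 restricts safety collection at the outset: "Only complications that could arise from the study specific intervention" are collected. It defines a complication broadly, as including "any unfavourable and unintended sign, symptom, or disease that is possibly related to the study intervention". Its musculoskeletal examples run "foot, knee, low back pain, arthritis, joint effusion, reduced joint function", and the list goes on to blood-pressure symptoms, vertigo, dizziness, breathing problems and mood alteration. Two things are then ruled out: ordinary muscle soreness and "conditions that were already present at the time of informed consent". No exception for worsening is attached, and none appears elsewhere in the protocol.

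Section 4.1 makes a diagnosis mandatory, "Chronic disease (musculoskeletal, neurologic, internistic", together with a self-reported history of imbalance.

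Section 1.3 reviews known harms. For eurythmy therapy (EYT) it cites "unspecific adverse reactions to EYT (like symptom aggravation, inner tension, depressed mood". For Tai Chi it states "Reported AEs were typically minor and expected, and primarily musculoskeletal related (e.g., knee and back pain".

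The safety analysis in section 14.5.2 is one sentence: "Rates of complications will be calculated with two-sided 95% CI". These rates serve objective 13 in section 2.1, which asks whether the two programmes do harm.

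**The concern.** In a population selected for chronic disease and imbalance, some of the harm from an exercise programme can be expected to appear as a known problem getting worse, such as a more painful arthritic knee or more frequent dizziness. A rule that sets aside anything present at consent, with nothing said about worsening, invites sites to leave such events off the complications form.

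The entry on that form is what matters. The rates are calculated from it and the DMC's regular report is on complications. An event not recorded at the site cannot be recovered at analysis. This is a rule for data collection, so a later statistical analysis plan could not repair it.

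**Working it through.** No planned figure is at issue, so the check sets the relevant sections side by side.

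**1. Do the exempt conditions overlap with the listed complications?** Section 6.3 records the baseline conditions and section 10.1.1 gives examples of complications.

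| Recorded at baseline (6.3) | Counterpart among the examples (10.1.1) |
|---|---|
| Arthritis of knee, hip or foot | Foot and knee pain, arthritis, reduced joint function |
| Vertigo | Vertigo, dizziness |
| Orthostatic and cardiovascular diagnoses | Symptoms of low or high blood pressure, arrhythmia, faintness |
| Pulmonary disease | Dyspnoea, bronchospasm |
| Mental condition | Mood alteration |

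The overlap is wide. For a patient who already has the condition, one section both names the clinical picture as a possible complication and exempts it. It gives no rule for deciding a flare.

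**2. Does another section settle it?**

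- *Section 10.1.2* has patients asked open questions about how they are. What is then documented is limited to complications as 10.1.1 defines them, so the exclusion still applies.
- *Section 10.1.3* asks for changes in severity to be followed, but only for an event already classed as a complication.
- *The relatedness rule in 10.1.1* allows an event to be called unrelated when another cause is the likelier explanation, even if the intervention cannot be ruled out. A flare of known disease is easily attributed to that disease, so this adds a second filter.
- *The FIMA questionnaire* (10.1.1, last paragraph) gives further safety information on service use at months 3, 6 and 12. In the reduced form described in 2.1 it asks about services used and place of living, not about individual events or their cause.
- *Sections 7.4 and 8.1* foresee marked deterioration of health, and 7.4 has the reason for ending treatment entered in the CRF. That records a reason for stopping, not a complication, and milder aggravation does not reach it.
- *The balance, cognition, depression and quality-of-life scales* (6.1) could show a group-level decline, but they are not counted as complications either.

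None of these closes the gap.

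**3. Can the size be derived?** Let f be the share of possibly related events that are aggravations of baseline disease, and d the share of those that sites leave out under the exclusion. Then

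reported rate = true rate × (1 − f × d).

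If every site records flares under the general definition, d = 0 and nothing is lost. If every site applies the exclusion literally, d = 1 and the relative loss is f. The protocol gives neither f nor d. Its nearest figure is in section 1.3: 13/419 = 3.1% of EYT patients with any unspecific reaction over 24 months. That figure pools all reactions, gives no share for aggravation and comes without a causality assessment, so it does not supply f.

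**The case against.** The best case against the point is that the exclusion concerns states and the definition concerns occurrences. An acute knee effusion after class, or a new spell of dizziness, was not present at consent and fits the general definition even in a patient with arthritis or known vertigo. The example list supports this reading. Reduced joint function describes a change, and much of the list would seldom apply in this population if every affected patient were exempt. Open questioning at visits should also bring such events to the site's attention.

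Much of this stands. A reader might infer that aggravation is never counted as harm, or that the rates are too low by construction. The documents do not support either statement: the text is silent on worsening, and a site may legitimately record a flare as a new occurrence. A reader might also infer that aggravation is the harm most to be expected, because section 1.3 names it first among EYT reactions. Order in a list of examples is not frequency, and the knee and back pain cited for Tai Chi is not described there as worsening of earlier disease.

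What does not stand is the suggestion that the matter is therefore settled. Two reasonable sites can read 10.1.1 in opposite ways, and the other channels do not feed the complication count.

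**Conclusion.** The point holds as an unresolved collection rule with a likely direction of bias. Read literally, section 10.1.1 omits possibly exercise-related aggravation of baseline disease. Read generously, it leaves each site to decide. Complication rates and DMC reports may therefore be too low or inconsistent between sites. The size cannot be stated: it lies between no loss and the whole share of events that are aggravations, and the protocol gives no figure for that share. That every patient has a chronic disease shows how widely the rule can apply, not how many complications it removes.

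The conclusion assumes that the complications form and site instructions follow 10.1.1 as written. The form and the DMC charter are not part of the protocol. The primary endpoint and its analysis are unaffected. The amendment should still be made, because the safety conclusion rests on these rates and there is no wider adverse-event record behind them.

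**What to change.** Reword the exclusion in 10.1.1 along these lines: *conditions already present at informed consent, unless they worsen in intensity or frequency after the start of the intervention and a relationship is possible*. As elsewhere in 10.1.1, intervention should include other exercise in the standard care arm. State that such worsening is documented as a complication and graded under 10.1.3. Add a tick box to the complications form for worsening of a pre-existing condition, and include these events in the rates and the DMC reports. The tick box also lets the rates be shown with and without them.

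The new clause should be reconciled with section 7.4, so that a deterioration entered as the reason for ending treatment is also assessed for the complications form.

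The cost is one clause, one form field and a short note to sites. There will be slightly more documentation, and the stated complication rates will look less favourable. The change affects recording only, not the treatment of patients.
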